#### **5.4. Concomitant Medication(s)**

Any medication that the subject takes other than the study drug specified in the protocol is considered concomitant medication. Information about concomitant medications will be recorded in the Case Report Form (CRF) from the screening visit through the EOT.

At the 2-week and 6-week FU Visits, only antifungal therapy the subject receives and the indication for use (eg, prophylaxis, treatment) will be recorded in the CRF. The use of non-absorbable antifungal drugs (eg, clotrimazole troches) is not required to be reported.

The recording of concomitant medications other than antifungal agents at these time points is not required unless the subject experiences an adverse event during the follow-up period, in which case all concomitant medications that the subject was receiving at the time of the adverse event must be recorded.

Treatment with another systemic antifungal agent [aside from oral nonabsorbable azoles (eg, clotrimazole troches) in not permitted, with the following exception: for the PK sub-study only (first 6 subjects aged 1 month to <2 years) administration of a second medication classified as an azole, polyene, or echinocandin will be allowed during the study treatment phase, at the Investigator's discretion.

## **6. STUDY PROCEDURES**

It is expected that all subjects will be hospitalized at the time study treatment is initiated, and will therefore be under continuous medical surveillance during the early period (if not all) of therapy.

Witnessed written parental or legal guardian consent and assent from the child or adolescent must be obtained prior to performing any screening procedures. Subject identification numbers will be assigned sequentially as subjects are screened into the study and these numbers will be retained throughout the study.

## 6.1. Screening Visit

The following screening activities will be performed following the informed consent and within two days prior to first dose.

- Obtain informed consent/assent (Note: no study procedures may be performed prior to obtaining written informed consent);
- Medical, surgical, and medication history (Please note: only antifungal medications that the subject was receiving within the past 30 days prior to enrolment are required to be recorded);
- Complete physical examination (including vital signs);
- Temperature;
- Assessment of signs and symptoms of *Candida* infection;
- Urine or serum pregnancy test (for females of childbearing potential);
- Fundoscopic examination;

**\*\* Please Note \*\*** Fundoscopic examination should be performed with pupils dilated if possible. In addition, when required by the protocol, the exam should be performed by an ophthalmologist unless it is not possible for practical reasons, in which case it may be performed by the principal investigator or subinvestigator. If it is not possible to perform a fundoscopic examination prior to the first dose of study drug, it may be performed within 48 hours of the first dose. Under extenuating circumstances, if a fundoscopic examination cannot be performed at baseline or within 48 hours, every effort should be made to perform the examination as soon as possible thereafter.

- Record screening blood and/or tissue (as clinically indicated) culture results (Note: If organism identity is pending, plan to record results on the case report form at a later time when the organism identity is determined and the results are available);
- Obtain blood sample for blood culture if the day of the screening visit is also Day 1 of treatment. Otherwise, a blood sample for blood culture is not required until the first day of treatment (Day 1), just prior to the administration of study drug;
- CBC with differential (Complete blood count with differential and RBC count with reticulocyte count and platelets count);
- Serum chemistry [Aspartate aminotransferase (AST), Alanine aminotransferase (ALT), Alkaline-Phosphatase (Alk-Phos), Total Bilirubin, Albumin, Bicarbonate, Glucose, Urea nitrogen (BUN), Creatinine (Cr), Sodium (Na), Potassium (K), Calcium (Ca), Chloride (Cl), and Magnesium (Mg)].

- For subjects with *Candida* endocarditis (not applicable to Korean and Portuguese investigator sites): Perform echocardiogram, either transesophageal (preferred) or transthoracic;

**\*\* Please Note \*\*** If an echocardiogram was already performed within the previous 96 hours (of the screening visit), then an echocardiogram at the time of screening is not required. In this case, the results of the echocardiogram used to support the diagnosis of *Candida* endocarditis will be reported in the case report form.

- For subjects with *Candida* osteomyelitis (not applicable to Korean and Portuguese investigator sites): Perform magnetic resonance imaging (MRI) study of affected area;

**\*\* Please Note \*\*** If an MRI was already performed within the previous 96 hours (of the screening visit), then an MRI at the time of screening is not required. In this case, the results of the MRI used to support the diagnosis of *Candida* osteomyelitis will be reported in the case report form.

It is noted that that it may be possible for the screening activities AND Day 1 (first day of study administration) to be the same day. This will be permitted in this protocol.

## 6.2. Study Period

### 6.2.1. Daily, Through End of Treatment

- Study drug administration: a loading dose of 3.0 mg/kg (not to exceed 200 mg) on Day 1, and a maintenance dose of 1.5 mg/kg (not to exceed 100 mg) subsequently;
- Record temperature (Note: Subjects receiving treatment in the outpatient setting may have less frequent assessments, but not less than at least once every 7 days. Close monitoring of subjects treated in the outpatient setting is required);
- Record Adverse Events and Concomitant Medications;
- Cultures of other normally sterile sites as clinically indicated.

### 6.2.2. Days 1 and 2 ONLY for Sub-study Subjects (first 6 subjects aged 1 month to <2 years at selected sites)

Prior to the administration of the first dose of study drug, a plasma sample (0.1 – 0.2 mL) should be obtained and sent to the reference laboratory to test for assay interference. Excess blood collected for safety laboratory testing may be used for this sample, otherwise it should be collected directly from the subject.

**Pharmacokinetic sampling:** Six (6) blood samples (0.3-0.5 ml each to provide 0.1 – 0.2 mL plasma) will be collected for anidulafungin measurement at the following time points:

- **On Day 1:** 2 minutes before the end of infusion;

- **On Day 2:** Just prior to the start of infusion; 2 minutes before the end of infusion, 6 hours after start of infusion, 12 hours after start of infusion, and 24 hours after start of infusion.
- In the event that the sample required 2 minutes before the end of infusion was not taken at the specified time, every effort must be made to acquire a sample within 5 minutes of the end of infusion with proper and specific time documentation.

Note: In case the subjects are not ready for serial pharmacokinetic sampling on this specific day, this can be re-arranged at a later date when they continue to receive 1.5 mg/kg daily maintenance dose of anidulafungin. The flexibility of the sampling time is also allowed as long as the actual time of collection is recorded in the CRF.

Ideally, the pharmacokinetic (PK) sampling would be taken from a different site/line than the one used for study drug infusion. However, at the discretion of the investigator and with appropriate flushing of the line to clear all drug residues, samples may be collected using the same line.

**\*\* Important Note \*\*** For subjects in whom the investigator has chosen to administer anidulafungin in combination with a second antifungal agent, these subjects will be discontinued from treatment following completion of pharmacokinetic sampling but will remain in the study for continued safety assessments and are required to return for the 2-week and 6-week follow-up visits.

For subjects in whom the investigator has chosen to administer anidulafungin as monotherapy, following completion of pharmacokinetic sampling these subjects will continued to be treated with anidulafungin for a minimum duration of 14 days from the time of the last negative culture (defined as the second of two consecutive negative cultures, separated by at least 24 hours, following the last positive culture) and improvement of clinical signs and symptom of candidemia or invasive candidiasis.

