### 5.2.3. Administration

Anidulafungin will be administered intravenously at an infusion rate not exceeding 1.1 mg/minute. Anidulafungin loading dose of 3.0 mg/kg (not to exceed 200 mg) on the first day of treatment should be administered intravenously at a rate of 1.1 mg/min or less, however the actual duration of infusion time should not exceed the calculated duration of infusion time (based on 1.1 mg/min) plus an additional 30 minutes. For example, for a child weighing 25 kg, the calculated duration of infusion time (based on a rate of 1.1 mg/min) would be 68 minutes, and maximum duration of infusion would be 98 minutes (68 minutes plus 30 minutes).

Anidulafungin maintenance dose of 1.5 mg/kg/day (not to exceed 100 mg) on subsequent days should be administered intravenously at a rate of 1.1 mg/min or less, however the actual duration of infusion time should not exceed the calculated duration of infusion time (based on 1.1 mg/min) plus an additional 30 minutes. For example, for a child weighing 25 kg, the calculated duration of infusion time (based on a rate of 1.1 mg/min) would be 34 minutes, and maximum duration of infusion would be 64 minutes (34 minutes plus 30 minutes).

**\*\* Important Note \*\* In subjects who already initiated on IV anidulafungin prior to study entry, a repeat loading dose is not required. Instead, these subjects may be initiated on maintenance doses of IV anidulafungin.**

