## 7.9. Pharmacokinetic Assessments

### 7.9.1. Blood Sampling for Subjects in the PK Sub-Study (1 Month to <2 Years of Age)

The first 6 children aged <2 years enrolled in the PK substudy (at selected centers) will undergo the PK sampling as described below.

Prior to the administration of the first dose of study drug, a plasma sample (0.1 – 0.2 mL) should be obtained and sent to the reference laboratory to test for assay interference. Excess blood collected for safety laboratory testing may be used for this sample, otherwise it should be collected directly from the subject.

Following initiation of treatment, blood samples (approximately 0.3 - 0.5 mL each) will be collected for anidulafungin measurement at the following 6 time points.

- On Day 1 (receiving 3 mg/kg IV infusion): 2 minutes before the end of infusion;
- **On Day 2 (receiving 1.5 mg/kg IV infusion):** Just prior to the start of infusion; 2 minutes before the end of infusion, 6, 12 and 24 hours after the start of infusion.

Due to the special conditions of the study population, the sampling time and day can be flexible in order to fit the subject's schedule. For instance, if serial pharmacokinetic sampling cannot be scheduled on Day 2, subjects will continue to remain on IV treatment to allow sample collection at a later date. The actual sampling time and date will be recorded in the CRF.

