## 9.3. Pharmacokinetic Analyses

### 9.3.1. Non-compartmental Pharmacokinetic Analysis

Non-compartmental pharmacokinetic analysis will be performed on individual plasma anidulafungin concentration-time data from children <2 years to obtain the following pharmacokinetic parameters of anidulafungin:  $AUC_{24}$  and  $C_{max}$ . Data listings and summary statistics will be generated for each pharmacokinetic parameter and presented in graphical and/or tabular format.

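### In the infant PK sub-study, a peak sample fixed at 2 minutes before the end of infusion understates Cmax by an amount that depends on weight and infusion rate

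*Protocol*

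**What the plan says.** Protocol 6.2.2 and 7.9.1 and Schedule of Activities footnote 19 put one near-peak sample on each of Days 1 and 2. For Day 2, 6.2.2 lists: "Just prior to the start of infusion; 2 minutes before the end of infusion, 6 hours after start of infusion", followed by 12 and 24 hours. Section 7.9.1 repeats the post-dose times as "2 minutes before the end of infusion, 6, 12 and 24 hours after the start of infusion". The 2-minute offset is the same at every weight. If that sample is missed, 6.2.2 says that "every effort must be made to acquire a sample within 5 minutes of the end of infusion". Sampling times may otherwise be moved if the actual time is recorded.

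Infusion time does depend on weight. Section 5.2.3 states: "Anidulafungin will be administered intravenously at an infusion rate not exceeding 1.1 mg/minute". It adds that "the actual duration of infusion time should not exceed the calculated duration of infusion time (based on 1.1 mg/min) plus an additional 30 minutes". Its worked example for a 25 kg child gives 68 minutes (maximum 98) for the loading dose and 34 minutes (maximum 64) for maintenance. It gives no example for an infant.

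Section 9.3.1 says "Non-compartmental pharmacokinetic analysis will be performed on individual plasma anidulafungin concentration-time data from children <2 years", to obtain AUC24 and Cmax. Section 2.2 lists Cmax at 1 month to <2 years as a secondary endpoint. Section 3 says these six subjects are used to confirm the regimen before the age group opens at all sites.

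**The concern.** A 2-minute offset hardly matters in a 90-minute infusion but can be a large part of an infusion that lasts a few minutes. While a short constant-rate infusion is running, the concentration is still rising, so a sample drawn before it stops can only understate the end-of-infusion level. The gap widens as weight falls and as the rate nears the cap. With six subjects, such a shortfall cannot be told apart from a real difference in exposure. It falls on a named secondary endpoint, in an age group whose pharmacokinetics section 1.3.2 describes as not yet characterized.

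**Working it through.** **Inputs from the documents.** Rate cap 1.1 mg/min and the 30-minute allowance (Protocol 5.2.3); doses 3.0 mg/kg on Day 1 and 1.5 mg/kg after that (6.2.1); 2-minute offset (6.2.2); distribution half-life 0.5-1 h and main elimination half-life about 24 h (1.3.2; not infant values).

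**Assumptions.** Weights of 3, 4 and 10 kg; constant infusion rate; distribution phase contributing 30-70% of the initial concentration after a dose. None of these is in the documents.

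**Step 1: reproduce the plan's figures.** Shortest infusion T = weight x dose / 1.1; longest = T + 30. At 25 kg, 75/1.1 = 68.2 min (maximum 98.2) and 37.5/1.1 = 34.1 min (maximum 64.1). Both match 5.2.3.

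**Step 2: share of dose delivered at the sample = 1 - 2/T.** For a 100 mg dose at the cap, T = 90.9 min and the share is 98%. For infants:

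| Day, weight | Dose (mg) | Shortest T (min) | Share in | Longest T (min) | Share in |
|---|---|---|---|---|---|
| Day 2, 3 kg | 4.5 | 4.1 | 51% | 34.1 | 94% |
| Day 2, 4 kg | 6 | 5.5 | 63% | 35.5 | 94% |
| Day 2, 10 kg | 15 | 13.6 | 85% | 43.6 | 95% |
| Day 1, 3 kg | 9 | 8.2 | 76% | 38.2 | 95% |
| Day 1, 4 kg | 12 | 10.9 | 82% | 40.9 | 95% |
| Day 1, 10 kg | 30 | 27.3 | 93% | 57.3 | 97% |

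**Step 3: from dose share to Cmax.** On Day 2, drug from the loading dose is already present, so the shortfall in Cmax is about (2/T) x (1 - trough/peak). A steady-state two-exponential model with the inputs above gives trough/peak of about 0.23-0.42 at the maximum rate.

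- 3 kg: 0.489 x 0.58 = 28% to 0.489 x 0.77 = 38%; full model 28-37%.
- 4 kg: 0.367 x 0.58 = 21% to 0.367 x 0.76 = 28%; full model 21-28%.
- 10 kg: 0.147 x 0.58 = 9% to 0.147 x 0.76 = 11%; full model 8-11%.
- Longest permitted infusion: full model 3-4% at 3 and 4 kg, 2-3% at 10 kg.

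On Day 1, with no earlier anidulafungin on board, the shortfall is at most 2/T: 24% at 3 kg, 18% at 4 kg and 7% at 10 kg, all at the maximum rate.

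**Step 4: can a later sample recover the peak?** Even after the longest 10 kg maintenance infusion (43.6 min), the 6-hour sample comes 316 min after the end. That is 5.3 distribution half-lives of 1 h, which leaves under 3% of the distribution phase. It cannot.

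**Step 5: side checks.** AUC24 by linear trapezoid (assumed; no rule is stated) is 6-11% low at 3 kg at the maximum rate and about 1% low at the longest infusion. A sample 5 minutes after the end would read 94-99% of the end-of-infusion concentration.

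**The case against.** The strongest reply is that 1.1 mg/min is a ceiling. A site that uses the full allowance delivers about 94% of a 3 kg infant's dose before the sample, and the error is then trivial. That stands. A reader might infer that the sample is generally drawn with only half to two-thirds of the dose in for the smallest infants. The documents do not support this. A share of one half needs T = 4 min and two-thirds needs T = 6 min, which on Day 2 means 4 x 1.1/1.5 = 2.9 kg to 6 x 1.1/1.5 = 4.4 kg at the maximum rate. Only the first 1.9 minutes (3 kg) or 0.5 minutes (4 kg) of the 30-minute allowance could be used. No weights are given and the six places have no age sub-quota, so whether any of the six falls in that range is unknown. Nor does half the dose mean half the Cmax, because of carry-over.

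A reader might also infer that the bias would lead the sponsor to confirm the wrong regimen or miss a high peak. No Cmax criterion for confirmation is stated, the objective is exploratory, exposure-response in 9.3.2 rests on AUC24, and the sampling scheme behind any older comparator is not given.

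Other points stand in part. SAP 2.2 sends this objective to a separate analysis plan that was not supplied; it may define Cmax and handle early samples. Section 9.3.1 does not itself say that Cmax is the highest observed value, though that is the usual convention. Actual sample times are already recorded, and SAP 8.2.4.5 needs infusion times for infusion-related events. The 5-minute fallback gives a nearly unbiased value if drawn after the end. It applies only when the planned sample is missed, however, so it mixes two kinds of peak value within six subjects.

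What remains is that following the primary instruction gives a low value, and the protocol text contains no correction. Section 3 describes the population analysis as covering all the other subjects.

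**Conclusion.** The concern holds in a limited form. Sub-study Cmax can only err low, and by an amount set by weight and by how each site runs the infusion. On Day 2 the error spans roughly 3% to 37% at 3 kg and 2% to 11% at 10 kg across the permitted infusion times; the effect on AUC24 is much smaller. The direction follows from the protocol's text and constant-rate infusion. The sizes rest on assumed weights, an assumed distribution share and half-lives not measured in infants. The documents show neither how often the upper end would occur nor that it would change the regimen decision. It is worth correcting because the endpoint is named, no later sample recovers the peak and the remedy is cheap.

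**What to change.** In Protocol 6.2.2, 7.9.1 and Schedule footnote 19, define the Day 1 and Day 2 peak sample as taken at the recorded end of infusion: immediately after it stops and no later than 5 minutes. Require actual infusion start, infusion stop and sample times in the CRF. For any sub-study infant sampled before the end, report the observed value with the share of dose delivered, and add a model-predicted end-of-infusion concentration based on actual times as a sensitivity estimate. Carry the same rule into the separate PK analysis plan.

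No change to dose or infusion rate is proposed, and the number and volume of samples stay the same. The cost is wording in three places, and a few values that carry a model-based companion estimate from a small sample.

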### 6.2.3. Days 1, 3, 5, 7 and 9 for ALL Subjects OTHER Than the Sub-Study Subjects Above

- Pharmacokinetic sampling for anidulafungin and polysorbate 80 measurements: Two aliquots of blood samples (one: approximately 0.3 - 0.5 mL for anidulafungin measurement; the other: approximately 1 mL for polysorbate 80 [a formulation excipient] measurement) will be collected at 3 – 5 of the following occasions during the study:
  - **Day 1:** post-dose (between 0 – 2 hours following the end of anidulafungin infusion);
  - **Day 3:** pre-dose (just prior to the start of the anidulafungin infusion);
  - **Day 5:** post-dose (between 0 – 3 hours following the end of anidulafungin infusion);

- **Day 7:** delayed post-dose (between 6 – 12 hours following the end of anidulafungin infusion);
- **Day 9:** pre-dose (just prior to the start of anidulafungin infusion).

Note: The above sampling days are flexible and could be modified at the discretion of each study center as long as samples are collected between Day 1 and the last day of IV treatment with anidulafungin with the actual time of collection documented in the CRF. If only 3 samples can be collected, preference is for the two post-dose and one delayed post-dose time points. The delayed post-dose sample may be collected prior to Day 7, for example on Day 3, to facilitate the preferred sample collection.

#### **6.2.4. Day 3**

- Targeted physical examination (including vital signs);
- Blood cultures (unless two consecutive blood cultures, separated by at least 24 hours, has been confirmed to be negative) (for subjects with microbiologically confirmed ICC);
- CBC with differential (same as in screening);
- Serum chemistry (same as in screening).

#### **6.2.5. Day 7**

- Targeted physical examination (including vital signs);
- Blood cultures (unless two consecutive blood cultures, separated by at least 24 hours, has been confirmed to be negative) (for subjects with microbiologically confirmed ICC);
- CBC with differential (same as in screening);
- Serum chemistry (same as in screening).

#### **6.2.6. Day 10**

- Targeted physical examination (including vital signs);
- Assessment of signs and symptoms of *Candida* infection.

#### **6.2.7. Days 11 to 34 (Day Prior to Last Day of IV Anidulafungin Therapy – Maximum is 35 Days on Anidulafungin)**

- Perform targeted physical examination (including vital signs) every 3 days (Note: Subjects receiving treatment in the outpatient setting may have less frequent assessments, but not less than at least once every 7 days. Close monitoring of subjects treated in the outpatient setting is required);

- CBC with differential every seven days (same as in screening);
- Serum chemistry every seven days (same as in screening).

### 6.3. End of IV Anidulafungin Therapy

The following assessments will be performed on the last day (or within 24 hours of the last day) of IV anidulafungin treatment:

- Targeted physical examination (including vital signs);
- Assess signs and symptoms of *Candida* infection;
- Fundoscopic examination, only if the baseline fundoscopic examination was abnormal;
- Blood cultures (for subjects with microbiologically confirmed ICC);
- Specimen culture (from other normally sterile sites as clinically indicated);
- CBC with differential (same as in screening);
- Serum chemistry (same as in screening);
- Echocardiogram, either transesophageal (preferred) or transthoracic (to be performed only in subjects with *Candida* endocarditis) (**not applicable to Korean and Portuguese investigator sites**);
- **\*\* Please Note \*\*** To be performed at the End of Treatment with IV anidulafungin in subjects who are not switched to oral fluconazole. In subjects who are switched to oral fluconazole, echocardiogram should be deferred to the End of Oral Therapy visit.
- Magnetic Resonance Imaging (MRI) study (to be performed only in subjects with *Candida* osteomyelitis) (**not applicable to Korean and Portuguese investigator sites**);
- **\*\* Please Note \*\*** To be performed at the End of Treatment with IV anidulafungin in subjects who are not switched to oral fluconazole. In subjects who are switched to oral fluconazole, echocardiogram should be deferred to the End of Oral Therapy visit.
- Evaluation of clinical and microbiologic response (See [Section 7.4](#)) (to be performed only in subjects with microbiologically confirmed ICC);
- Urine or serum pregnancy test (for females of childbearing potential) to be done at the End of Treatment period in subjects who are not switched to oral therapy.
- Record adverse events and concomitant medications.

